### **3.8 Study Termination**

The study can be prematurely or temporarily stopped or terminated, either at local or national level, at the request of Ethics Committees, Competent Authorities or the Sponsor.

The study may also be put on hold or even terminated by the Study Steering Committee, for safety, ethical or other reasons, at the request of Adverse Event Committee.

The study is terminated/has ended when:

- The sample size has been reached AND
- Follow up period has been completed AND

- The Database has been cleaned AND
- A Close Out visit has been performed AND
- Appropriate communication has been distributed AND
- The Final report has been provided.

After the study closure, the patients will be managed following the standard medical care.

## 4 Scientific Soundness

### 4.1 Sample Size

Study aim is to assess/explore, in a cohort of STEMI patients at 1 year of follow-up from primary PCI, if categorization of IMR based on the median value can be considered a predictive / prognostic for the occurrence of cardiovascular events such as death, re-MI, re-hospitalization for HF, resuscitation or appropriate ICD shocks.

It is believed, based on the events reported in similar cohort of patients , that the expected events at one year should be of 12-16%.

The present study aims to demonstrate that the incidence of events is significantly different in the two subpopulations of patients with IMR upper and lower of the value of 32, found by Fearon et al.; other authors found the median value as event predictor.

Based on these assumptions, hypothesizing an incidence of events/year by 7% in the group of patients with IMR values below its median and 21% in the group with higher values of IMR, with an alpha error = 0.05, a power of 85% and applying the two tails Chi-square test, it is estimated that 218 patients are needed.

Providing a dropout rate of 10%, the number of patients who must be enrolled will be 242.

It is assumed that the participant centers will be up to 20. Based on number of cases in previous year evaluation, enrollment mean rate is assumed to be approximately 6-10 patients/year/center.

### 4.2 Statistical Methods

Data analysis will begin when all patients enrolled in the specified period will have completed 12 months of follow-up.

#### Descriptive statistics:

Continuous variables will be described by means of position indexes (mean, median, quantiles that best fit the needs of data analysis) and index of dispersion (standard deviation, interquartile distance, range).

Categorical variables will be described using absolute frequencies and relative frequencies rates.

The 95% confidence intervals (CI 95%) will accompany study parameters estimations.

Graphical representation (box plots, histograms, etc...) will complement the descriptive analysis.

#### **Primary Objective Analysis:**

The Chi-square test will be used to evaluate the existence of associations between IMR-values (above and below the median) and the outcome.

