### 2.4 Study Design

This is a prospective, multicenter study designed to evaluate IMR ability to predict events occurrence, defined as Cardiovascular death, re-MI, re-hospitalization for HF, resuscitation or ICD appropriate shock, during a 1 year follow-up period.

[figure not shown]
Patients will be enrolled in the study at hospital admission after the pathology assessment has been done. All participants will have the culprit lesion treated following clinical practice and guidelines ; Fractional Flow Reserve (FFR) and IMR will be measured after the primary PCI procedure to evaluate treatment success and myocardial viability. Non-culprit lesions will be functionally evaluated through FFR index and will be treated if FFR will show functional stenosis . FFR and IMR will be measured to evaluate treatment success and myocardial viability. Patients will be followed-up at 1m, 6m and 1y periods.

Device used to assess FFR and IMR is already in use in clinical practice at participating centres. The wire is used following indication for use (IFU), guidelines and clinical practice in the selected centers.

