### 3 Protocol Description

#### 3.1 Overview

The following table lists study activities that are performed at each scheduled visit.

Table 2: Activities performed at each scheduled visit

Visit	When	Type	Activities
Enrollment & Procedures & Predischarge	In Hospital Visits	In-Clinic	
 
▪ Patient Eligibility
 
▪ Patient Informed Consent
 
▪ Patient Demographics
 
▪ Patient Physical Examination
 
▪ Patient Cardiovascular History
 
▪ Patient Medical History
 
▪ Risk and Functional Classifications
 
▪ Patient Current Cardiac Medications
 
▪ Cholesterol/Triglycerides/Enzymes+
 
▪ Echocardiography
 
▪ 12-Lead ECG
 
▪ Procedure data
 
▪ Discharge evaluation
 
▪ Adverse Events *
 

1M Follow Up	$30 \pm 7$ days post-primary PCI	In-Clinic	
 
▪ Patient clinical status and medication
 
▪ Cholesterol/Triglycerides/Enzymes+
 
▪ NYHA & CCS class assessment
 
▪ Adverse Events *
 

6M Telephone Follow Up	$183 \pm 14$ days post-primary PCI		
 
▪ Patient clinical status and medication
 
▪ NYHA & CCS class assessment
 
▪ Adverse Events *
 

12M Follow Up	$365 \pm 14$ days post-primary PCI	In-Clinic	
 
▪ Patient clinical status and medication
 
▪ Cholesterol/Triglycerides/Enzymes+
 
▪ NYHA & CCS class assessment
 
▪ Echocardiography
 
▪ Adverse Events *
 

\*: If applicable

+: refer to table 1 for timing and details

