### **3.5.3 Procedure for assessing, recording and reporting Adverse Events, Adverse Device Effects, Serious Adverse Events and Serious Adverse Device effects**

Safety surveillance and reporting will be done for all patients enrolled in this study.

Safety surveillance within this clinical investigation and safety reporting, both performed by the investigator, starts as soon as the patient is enrolled in this clinical investigation (date of signature of the informed consent). The safety surveillance and the safety reporting will continue until the last follow-up visit has been performed or the patient is deceased or the patient/investigator concludes his participation into the clinical investigation.

NOTE: If an adverse event is documented at the patient's last follow up visit, both the notification and follow-up information on the AE CRF are to be provided to the sponsor.

- All serious Adverse Events and all Adverse Device Effects (serious or non-serious) are to be documented and reported to the sponsor maximum 3 calendar days after becoming aware of the event.
- Non-serious adverse events documentation and reporting are limited to cardiovascular and neurovascular events and to events endpoints related.

Should an AE occur, record AE information in the hospital records, document the information into the adverse event form as soon as possible. By completing the form, the sponsor will be notified. Refer to Table 1: Data Collection and Appendix F for Data Collection Method. In case of EDC failure, notify Sponsor via Fax ([contact]) or via [[contact]](mailto:[contact]).

Sponsor will be responsible for ensuring the assessment of immediate AE 'reportability' or 'non-reportability' to the competent authorities. All the reported AEs will be documented and reported in a periodic report.

Additional information may be requested, when required, by the sponsor in order to support the reporting of AEs to regulatory authorities and to support AE analysis. The investigator must notify the EC, if appropriate, in accordance with national and local laws and regulations, of the AEs reported to the sponsor.

In case of disagreement between sponsor and investigator in the AE assessment, then both assessments will be reported.

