### **3.6 Early Conclusion of Patient Participation**

All reasonable efforts should be made to retain subjects within the clinical trial until completion of the required period of participation. In addition to withdrawal following completion of the clinical trial, reasons for withdrawal include, but are not limited to the following:

- Patient and/or Family Request
- Patient Lost to Follow-Up
- Patient Withdrawn by Investigator
- Patient Withdrawn by Sponsor
- Patient Death

In case of withdrawal the Sponsor will be notified filling the Termination eCRF.

All information entered in the eCRF is authorized by the principal investigator or delegate. (Refer to "Appendix F for Data Collection Method" and refer to "Appendix G for Case Report Form" for information regarding patient data collected for this investigation).

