#### **Secondary Objective Analysis:**

IMR analysis as a possible predictive index will initially be carried out by evaluating whether there are quantiles that better identify classes of patients with higher risk of defined major cardiac event.

Discriminant model (ROC curve) will allow to assess whether there are IMR-threshold values (cut-off) to allow classification of patients at increased or decreased risk of future events.

The analysis of variance (ANOVA) for repeated measures or the analysis of covariance (ANCOVA) to multiple factors will be used to assess whether there are significant changes in continuous parameters during post-intervention.

Kaplan-Meier analysis of event-free survival (EFS) allows the assessment of possible risk factors (gender, age, smoking, cholesterol, etc...) testing the significance by log-rank test.

The significant results and other factors considered clinically relevant will be included, as independent variables in a Cox regression model having the appearance or not of composite event and the time as dependent variables.

Where multiple comparisons will be assessed, corrections for multiple comparisons will be applied and specified as needed.

Values of  $p < 0.05$  are considered statistically significant.

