#### **Ad-interim analysis**

Ad-interim reporting, providing the summary tables, may be performed if necessary or required by CIs and/or investigators, or project leader.

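### The yes/no primary test has no rule for patients lost before one year; fix the rule and pre-specify a time-to-event comparison by IMR group

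*Combined protocol and SAP*

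**What the plan says.** - **Primary analysis (4.2).** One sentence: "The Chi-square test will be used to evaluate the existence of associations" between IMR above or below the median and the outcome. The outcome (2.2.1) is a composite at one year that includes cardiovascular death.
- **Dropout (4.1).** "Providing a dropout rate of 10%, the number of patients who must be enrolled will be 242". The figure before inflation is 218. Dropout is not defined.
- **End of participation (3.6).** The text says that "reasons for withdrawal include, but are not limited to the following". The list that follows includes loss to follow-up and death, and no counting rule is attached.
- **Event recording (3.5.3).** "The safety surveillance and the safety reporting will continue until the last follow-up visit has been performed or the patient is deceased", or until participation is ended. Events before loss are therefore on file.
- **Final visit (Table 2).** Day 365 with a window of 14 days either side.
- **Time-to-event methods (4.2, secondary).** "Kaplan-Meier analysis of event-free survival (EFS) allows the assessment of possible risk factors", with a log-rank test and then a Cox model on the composite. The example factors are patient characteristics and the list is open; IMR group is not named.
- **Start of analysis (4.2).** After all enrolled patients have completed 12 months. Nothing is said about those who do not.
- **Interim tables (4.2).** "Ad-interim reporting, providing the summary tables, may be performed if necessary".

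No section defines an analysis population, the handling of missing outcomes, or censoring.

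**The concern.** Three counting rules fit the text:

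- **(a)** drop every lost patient;
- **(b)** keep every lost patient and count those without a recorded event as event-free;
- **(c)** keep a lost patient only if an event was recorded.

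They give different answers from the same data, and the number of lost patients is of the same order as the number of events. Rule (a) also discards primary events that are already on file. A rule left open can be chosen after the results are known, and in a study with a single primary test the reader could not tell. Meanwhile a method that uses all follow-up is already in the plan but is not directed at the primary question.

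**Working it through.** **1. The plan's own figures.** Inputs from 4.1: 7% and 21%, two-sided alpha 0.05, power 85%; a median split gives 1:1. The pooled mean is 14%.

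n per group = [1.960·√(2·0.14·0.86) + 1.036·√(0.07·0.93 + 0.21·0.79)]² / 0.14² = 108.7, so 109 per group and 218 in total. Then 218/0.90 = 242.2, stated as 242. Both figures reproduce. Power is 85.1% with 109 per group and 88.6% with 121.

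**2. Scale.** Lost: 0.10 × 242 = 24. Expected events: 0.14 × 242 = 34.

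**3. Hand check.** Assume a constant hazard and loss spread evenly over the year, so that a lost patient is followed for about half the year's risk. Loss is unrelated to outcome.

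Equal 10% loss:
- (a) about 21 − 7 = 14.0 points.
- (b) the factor is 0.90 + 0.10/2 = 0.95, so 19.95 − 6.65 = 13.3.
- (c) 19.95/(0.90 + 0.10 × 0.105) − 6.65/(0.90 + 0.10 × 0.035) = 21.9 − 7.4 = 14.5.
- Events deleted by (a): 12.1 × (0.105 + 0.035) = 1.7.

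Loss of 5% (low IMR) and 15% (high IMR):
- (b) 21 × 0.925 − 7 × 0.975 = 19.4 − 6.8 = 12.6.
- (c) 19.4/(0.85 + 0.15 × 0.105) − 6.8/(0.95 + 0.05 × 0.035) = 22.4 − 7.2 = 15.3 before rounding.

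**4. Simulation.** 20,000 trials per scenario, 121 per group. Event times are Weibull with shape 0.5 (early-weighted) or 1.0 (constant hazard), loss times are uniform over the year, and final visits are uniform over days 351-379. Ranges cover both shapes. The true difference is 14.0 points.

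| Loss low/high IMR | (a) | (b) | (c) | Kaplan-Meier |
|---|---|---|---|---|
| 10/10%, independent | 13.9-14.0 | 13.2-13.5 | 14.5-14.7 | 14.0 |
| 5/15%, independent | 13.9 | 12.6-13.1 | 15.2-15.7 | 14.0 |
| 10/10%, risk-related | 13.0-13.1 | 12.9-13.3 | 13.9-14.3 | 13.6-13.7 |
| 5/15%, risk-related | 11.8 | 11.8-12.5 | 14.0-14.7 | 13.0-13.3 |

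Risk-related means that a patient with an event within the year is twice as likely to be lost. Only the 10% overall loss comes from the plan; unequal and risk-related loss are hypothetical. In the last row (c) lands near 14 only because two errors offset each other.

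**5. Power.**
- Equal independent loss: (a) 86.0-86.6%, (b) 87.5-88.7%, (c) 87.7-88.7%, log-rank 87.7-89.0%. Rule (a) deletes 1.8-2.3 recorded events.
- Risk-related 10/10%: (a) 84.2-84.5%, log-rank 87-88%.
- Risk-related 5/15%: (a) about 77%, log-rank 84-87%.

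**6. Loss reversed (15% low, 5% high, independent).** (b) 13.9-14.0, (c) 13.7-13.8, Kaplan-Meier about 14.0. In a separate run with exponential event and loss times, power in this case was 90.5% for (b), 84.2% for (c) and 87.7% for log-rank. With 5/15% it was 84.9%, 91.2% and 88.7%.

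**7. Type I error.** Near 5% throughout: up to about 5.8% with unequal independent loss (rule (c)), and about 6% at most with risk-related loss.

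**8. Smaller items.** Counting visits from day 351 as complete lowers the difference by about 0.1 point. Censoring non-cardiovascular death instead of treating it as competing, at an assumed 1-3%, gives at most 21.35% and 7.11%. The difference then changes by 21.35 − 7.11 − 14.00 = 0.24 points.

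**The case against.** The case for leaving the plan alone has weight. The endpoint is fixed at one year and the study is sized for a chi-square, so test, endpoint and sample size agree. Inflating 218 to 242 suggests that dropouts contribute nothing, which points to rule (a), and (a) is nearly unbiased when loss is unrelated to outcome. At the plan's own 10% loss, if equal and independent, log-rank gains about 2 power points over (a) and 0-0.3 over (b) and (c). Enrolment began in June 2013 (2.6), so replacing the primary test is a mid-study change. The factor list in 4.2 is open and could include IMR.

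Most of this stands and limits the weight of the point. It does not close the gap. A sizing allowance is not an analysis rule, and applied literally it would remove recorded primary events. An open factor list does not commit anyone to an IMR-group comparison.

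Some stronger readings go further than the documents:

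- **The study is underpowered.** It is not: 218 and 242 reproduce, and with equal independent loss every rule meets 85%. Power below 85% appears only under hypothetical unequal or risk-related loss.
- **The chi-square is invalid.** Type I error stays near 5%.
- **Deaths would be excluded because 3.6 lists death among the withdrawals.** Cardiovascular death is a primary event in 2.2.1, so that reading is unlikely; the plan should simply say so.
- **Interim tables will show outcome by IMR group.** The text mentions summary tables only and does not describe their content.
- **Rules (b) and (c) bracket the Kaplan-Meier estimate.** They do not when loss is higher in the low-IMR group.

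**Conclusion.** The point holds as a recommended improvement. The primary analysis has no rule for about 24 expected dropouts, and a better use of their follow-up is already in the plan but is not applied to IMR group. With equal independent loss the consequence is small: at most about 0.8 points either way on a difference of 14.0, with planned power met. With hypothetical 5/15% independent loss, rules (b) and (c) miss by up to 1.4 and 1.7 points in opposite directions, while Kaplan-Meier stays near 14.0. With hypothetical 5/15% risk-related loss, dropping lost patients gives about 11.8 points and about 77% power, against 13.0-13.3 and 84-87% for Kaplan-Meier and log-rank.

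A reader might infer that the time-to-event analysis removes the problem. It does not: it also assumes that loss is unrelated to outcome within group, so it is less biased but not unbiased. The sizes rest on the assumed timing of loss, the assumed hazard shapes and the hypothetical loss patterns; the plan gives only the overall 10%.

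**What to change.** Add to the time-to-event methods in 4.2 a pre-specified comparison of the IMR groups, and state:

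- **Comparison:** time to first composite event by log-rank or Cox, with one-year cumulative incidence by group and the difference, each with a 95% CI.
- **Time zero and IMR value:** the culprit-vessel measurement. Section 2.4 says "IMR will be measured after the primary PCI procedure to evaluate treatment success and myocardial viability", and 2.2.1 already times mortality from it. Section 3.2.1 also measures IMR at the staged procedure, so the value used should be named.
- **Events and censoring:** cardiovascular death is an event, non-cardiovascular death is a competing event, and lost or withdrawn patients are censored at last contact. Say how deaths of undetermined cause (Appendix A) count.
- **End of the year:** event-free patients seen on days 351-364 are censored at that visit, and events after day 365 do not count.

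Make this the primary analysis if the amendment is in place before any table of outcome by IMR group is produced, and keep the chi-square as a sensitivity analysis. Otherwise keep the chi-square primary with one named counting rule that retains events recorded before loss, count visits from day 351 as complete, and report the time-to-event result beside it as the pre-specified sensitivity analysis. Either way, do not present (b) and (c) as bounds on the Kaplan-Meier estimate. The choice of IMR cut-off (the median, or the value of 32 in 4.1) is a separate matter.

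**Cost.** A protocol amendment with ethics committee approval (6.3), a restated rationale in 4.1 if the primary test changes, and a little more analysis. The planned Cox model already needs event times; last-contact dates should be confirmed in the eCRF. No extra patients or procedures are needed, and the sample size stays at 242.

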#### **Secondary Objective Analysis:**

IMR analysis as a possible predictive index will initially be carried out by evaluating whether there are quantiles that better identify classes of patients with higher risk of defined major cardiac event.

Discriminant model (ROC curve) will allow to assess whether there are IMR-threshold values (cut-off) to allow classification of patients at increased or decreased risk of future events.

The analysis of variance (ANOVA) for repeated measures or the analysis of covariance (ANCOVA) to multiple factors will be used to assess whether there are significant changes in continuous parameters during post-intervention.

Kaplan-Meier analysis of event-free survival (EFS) allows the assessment of possible risk factors (gender, age, smoking, cholesterol, etc...) testing the significance by log-rank test.

The significant results and other factors considered clinically relevant will be included, as independent variables in a Cox regression model having the appearance or not of composite event and the time as dependent variables.

Where multiple comparisons will be assessed, corrections for multiple comparisons will be applied and specified as needed.

Values of  $p < 0.05$  are considered statistically significant.

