#### Secondary Objectives

Evaluation of:

- A better cut-off of IMR for the prognosis of study patients
- New CHF during index hospitalization

- Left Ventricular remodeling
- Incidence of new revascularization
- Incidence of stent thrombosis
- ST Resolution or residual ST elevation
- Possible predictors of patient outcomes

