### 2.2.2 Secondary Endpoints

- Evaluation of a better cut-off of IMR index based on primary endpoint events
- New CHF during index hospitalization
- Left Ventricular (LV) remodeling @ 1y (improvement of EF%, LVESV, LVEDV, LVEDD, LVESD, 16 segments WMSI and mitral insufficiency, assessed by TTE)
- Need for new revascularization @ 1y (revascularization yes/no)
- Stent thrombosis @ 1y (thrombosis yes/no)
- ST resolution or residual ST elevation post PCI (Electrocardiographic ST-segment elevation in two or more contiguous electrocardiogram (ECG) leads)
- Evaluation of possible events predictors including but not limited to age, sex, infarct area, Killip risk, number of PCI

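### The improved IMR cut-off is chosen and assessed on the same 26-35 expected events with no internal validation, so its apparent accuracy will on average be optimistic

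*Combined protocol and SAP*

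**What the plan says.** Section 2.1 lists first among the secondary objectives "A better cut-off of IMR for the prognosis of study patients", and section 2.2.2 lists first among the secondary endpoints "Evaluation of a better cut-off of IMR index based on primary endpoint events". The threshold is therefore to be derived from this cohort's own outcome events.

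Section 4.2, Secondary Objective Analysis, describes two steps. The first is "evaluating whether there are quantiles that better identify classes of patients with higher risk of defined major cardiac event". The second is the ROC step: "Discriminant model (ROC curve) will allow to assess whether there are IMR-threshold values (cut-off) to allow classification of patients at increased or decreased risk". The number and position of the quantiles are not given, and neither is the rule for picking a point on the ROC curve or the accuracy measure to be reported.

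Two general statements come closest to a safeguard. For multiple comparisons, "corrections for multiple comparisons will be applied and specified as needed" (Secondary Objective Analysis). For estimates, "The 95% confidence intervals (CI 95%) will accompany study parameters estimations" (Descriptive statistics).

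Section 4.1 supplies the scale: "the expected events at one year should be of 12-16" per cent, and "hypothesizing an incidence of events/year by 7% in the group of patients with IMR values below its median and 21" per cent above it, with 218 evaluable patients.

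**The concern.** A threshold picked because it separates events from non-events best in one sample benefits from the chance features of that sample. Its sensitivity and specificity in the same patients will on average exceed what it would achieve in new patients. The fewer the events, the larger the effect, and here there are about 30.

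Neither general statement in section 4.2 removes this. A multiplicity correction acts on p-values, not on the estimated accuracy of a selected threshold. A confidence interval describes sampling error around the apparent value, and the plan does not say that its intervals will allow for the selection.

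At stake is the reading of one secondary result: a reader would expect the new cut-off to identify more of the patients who go on to have an event than it would in practice.

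**Working it through.** **1. The plan's own figures.** With 7% and 21%, the mean rate is 14%. The pooled two-proportion formula gives n per group = [1.960 × √(2 × 0.14 × 0.86) + 1.036 × √(0.07 × 0.93 + 0.21 × 0.79)]² / 0.14² = (0.962 + 0.498)² / 0.0196 ≈ 108.7, hence 109 per group and 218 in all. This matches section 4.1. Dropout: 218/0.9 = 242.2, against the stated 242.

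**2. Expected events.** 218 × 0.12 = 26.2; 218 × 0.14 = 30.5; 218 × 0.16 = 34.9. At 30.5 events, one event is worth 1/30.5 = 3.3 points of sensitivity.

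**3. Assumptions the plan does not supply.** Two marker models were used, each reproducing 7% and 21% either side of the median:
- logistic: logit(risk) = −2.033 + 0.806z, with z standard normal;
- step: risk 7% below the median and 21% above it.

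The main selection rule was Youden: choose the c that maximises Se(c) + Sp(c) − 1. Apparent sensitivity is the share of the sample's events above the chosen c. True sensitivity is the population value at that same c. Optimism is the mean of apparent minus true.

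**4. Main result** (20,000 simulated studies per model, N = 218, 14% events, full ROC, Youden rule).
- Logistic: apparent 70.7%, true 62.5%, optimism 8.3 points (unrounded inputs); overstated in 87% of studies.
- Step: apparent 75.1%, true 68.4%, optimism 6.6 points (unrounded inputs); overstated in 80%.
- In events: 0.083 × 30.5 = 2.5 and 0.066 × 30.5 = 2.0.

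**5. Optimism in sensitivity by search rule and event rate (points).**

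| Search | Logistic | Step |
|---|---|---|
| Full ROC, Youden, 12% events | 9.2 | 7.5 |
| Full ROC, Youden, 14% | 8.3 | 6.6 |
| Full ROC, Youden, 16% | 7.5 | 5.8 |
| Full ROC, closest to (0,1), 14% | 6.0 | 5.9 |
| Best of 5 quantile cuts, Youden, 14% | 4.9 | 3.3 |
| Best of 5 quantile cuts, chi-square, 14% | 4.9 | 4.1 |
| Median fixed in advance, 14% | 0.3 | 0.3 |

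The five cuts are the 25th, 33rd, 50th, 67th and 75th percentiles. Over tertile, quartile and decile grids the range is 2.0-6.3. A separate simulation, with a binormal marker and its own step model, gave 8.9, 8.1 and 7.3 (binormal) and 7.3, 6.1 and 5.4 (step) at 12, 14 and 16%. Together the full-ROC Youden range is 5.4-9.2. The fixed-median row shows that the search causes the optimism.

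**6. Other measures** (full ROC, Youden, 14%).
- Specificity: optimism 1.1 (logistic) and 0.7 (step) points.
- Event rate above the cut: 27.4% apparent against 24.1% true (logistic), 22.7% against 20.7% (step), so 3.3 and 2.0 points.
- Event-free rate below the cut: about 2 points.
- AUC: 0.707 against 0.708 (logistic), 0.646 against 0.645 (step), so none. A single marker is not fitted, and the AUC does not depend on a chosen threshold.

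**7. Against sampling error.** The mean Wilson half-width for sensitivity is 14.7 and 14.3 points. Optimism is 8.3/14.7 = 56% and 6.6/14.3 = 46% of it.

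**8. What a bootstrap recovers** (2,000 studies, 300 resamples each, search repeated). Logistic: apparent 70.8%, corrected 65.2%, true 62.6%, so 5.6/8.2 = 68% of the optimism is removed. Step: 75.1%, 70.2%, 68.4%, so 4.9/6.7 = 73%.

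**The case against.** The best defence is that the aim is modest and the effect smaller than the noise. Section 4.2 asks only whether thresholds exist and calls IMR a possible predictive index. Section 2.1 ties the objective to the study's own patients. No section says the cut-off will be recommended for use elsewhere, and being listed first does not establish a hierarchy. The plan promises no sensitivity estimate, and sensitivity shows the largest optimism of the measures checked; specificity moves little and the AUC not at all.

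Most of this stands, and it limits the size and weight of the point. It does not remove the point. The documents nowhere label the new cut-off exploratory, the ROC step is meant to classify patients by future risk, and section 5.2 hopes IMR information will help future patients. Sampling error is larger, but it works in both directions and an interval displays it; the optimism runs mostly one way.

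Three stronger readings are tempting and not supported:
- A reader might infer one definite figure for the optimism. With no rule, marker distribution or accuracy measure in the plan, only a conditional range can be given.
- A reader might infer that the promised 95% intervals will be wrong. The plan does not say how they will be computed. In simulation, a standard interval for sensitivity covered 88-92% after a full Youden search but 92-96% after a quantile search, so this depends on choices not yet made.
- A reader might infer that the primary result is compromised. The primary analysis in section 4.2 is a chi-square test at the median, which is not chosen by outcome.

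**Conclusion.** The point holds as a cheap improvement to a secondary analysis. As written, the plan selects the cut-off and assesses it on the same 26-35 expected events without internal validation, so the selected cut-off's apparent accuracy is optimistic on average.

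At the plan's 7%/21% effect and 12-16% events, the optimism in sensitivity is about 5-9 points under a full-ROC Youden search and about 2-6 points if only a few quantiles are searched. For specificity it is about 1 point. These sizes rest on the assumed selection rules and marker shapes. The direction does not: every outcome-driven search examined overstated sensitivity on average.

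**What to change.** In section 4.2, Secondary Objective Analysis:

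1. Prespecify the criterion for selecting the cut-off and the quantiles to be examined.
2. Report the selected cut-off's sensitivity, specificity and any event rates by class with a bootstrap optimism correction that repeats the whole quantile and ROC search in each resample. Show the apparent values alongside.
3. Label the cut-off exploratory pending external validation.

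The cost is a few lines of text and some code, with no new data. The reported accuracy will look less favourable. The correction is also partial: in simulation it removed about 70% of the optimism in sensitivity, which is a further reason for the exploratory label.
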